| 1.0 | 1. SYNOPSIS 2. AIMS 3. STUDY DESIGN 4. ELIGIBILITY CRITERIA 5. TREATMENT DESIGN 6. SCHEDULE (STUDY VISITS) | 1. CHANGED AIMS (ADDED ASSOCIATIVE MEMORY, ADAPTED EVERYTHING ACCORDING TO CLINICALTRIALS.GOV), CHANGED OUTCOMES AND STATISTICAL PLAN ACCORDINGLY; CHANGED EXCLUSION (NO AD8 DUE TO ALREADY HIGH COUNT OF QUESTIONNAIRES) 2. CHANGED AIMS ACCORDING TO CLINICALTRIALS.GOV. MADE SLEEP MORE CONCRETE (ONLY SPINDLES AND SLOW WAVES ARE OUTCOMES); OTHER NEUROPSYCHOLOGICAL OUTCOMES THAN MEMORY SECONDARY OUTCOMES ([name] THINKS IT IS OKAY) 3. ADDED TELEPHONE CONTACTS EXPLICITLY; CHANGED ELECTRODES TO F7/P7 AND F8/P8 4. No AD8 5. ADDED WORD ASSOCIATION TEST 6. ADDED ASSOCIATIVE MEMORY, CHANGED QUESTION ABOUT ALCOHOL AND PSYCHOTROPIC SUBSTANCES/DRUGS FOR FOLLOW-UP VISITS (NOT LAST 3M, BUT LAST 24H), RVDLT ONLY DURING VISIT 2, AND RECALL IMMEDIATELY AFTER ENCODING (TO WIN TIME FOR ANALYSIS OF Y-FREQUENCY) | |
| 1.1 | 1. MEASUREMENT DESIGN, ENROLLMENT, STUDY DESIGN 2. EVERYWHERE 3. SECTION 7 | 1. RVDLT FOR Y-FREQUENCY ON VISIT 1 INSTEAD OF VISIT 2 (TO HAVE MORE TIME FOR ANALYSIS) 2. CHANGED PHONEMATIC/VERBAL FLUENCY TO LETTER FLUENCY (TO HAVE THE SAME VOCABULARY) 3. CHANGED TIMEPOINT OF VISIT 5 FROM DAY 5-9 AFTER STIMULATION TO DAY 6-9 AFTER STIMULATION (VISIT 4 AND 5 NOT ON THE SAME DAY, AND VISIT 4 ALREADY ON DAY 5 AFTER STIMULATION) | |
| 1.2 | | 1. 4 HOURS OF SLEEP EEG IS NOT AN EXCLUSION CRITERIA (WE WANT TO FIND OUT HOW MANY MANAGE TO DO IT) 2. NOT SHAM, BUT CONTROL FREQUENCY (21 Hz – 10 Hz WORSENS AUDITORY ATTENTION, 20 Hz IS HARMONIC; ALSO: CLOSER TO 40 Hz, THEREFORE SIMILAR SIDE EFFECTS, BUT NOT YET GAMMA). TEXT FROM MODIFICATION: WE ARE NOW TIGHTENING THE SCIENTIFIC CONTRAST SUCH THAT WE CAN DRAW CONCLUSIONS ABOUT THE EFFECT OF A SPECIFIC STIMULATION FREQUENCY, | |

| | | |
|--|--|--|
| | 
WHEREAS OUR PREVIOUS DESIGN ONLY ALLOWED TO DRAW CONCLUSIONS ABOUT THE EFFECT OF STIMULATION IN GENERAL. THUS, WE NOW USE A CONTROL FREQUENCY OF 21Hz INSTEAD OF THE ACTIVE SHAM STIMULATION.
 
3. tACS AMPLITUDE IS INDIVIDUALIZED (SAME AMPLITUDE FOR BOTH CONDITIONS; HAS TO BE SUPPORTED FOR 1h, THRESHOLDING FOR 21 AND 40 Hz, LOWER AMPLITUDE IS TAKEN)
 
4. NO INDIVIDUALIZED GAMMA, BECAUSE NO CLEAR/SINGLE PEAK DURING RVDLT ACCORDING TO [name]'S ANALYSIS
 
5. ELECTRODE POSITIONING FOR LEAST SIDE EFFECTS: T7/8, P7/8
 
6. ACTIGRAPHY ADDED TO SEE IF STIMULATION CHANGES ACTIVITY PATTERN. TEXT FROM MODIFICATION: ACTIGRAPHY: WEARING AN ACTIGRAPHY WRISTBAND. PARTICIPANTS ARE ASKED TO WEAR A WRIST-WORN ACCELEROMETER FROM VISIT 1 TO VISIT 6. THE DEVICE RECORDS REST AND ACTIVITY PHASES BY MEANS OF AN ACCELEROMETER, THUS ALLOWING CONCLUSIONS TO BE DRAWN ABOUT THE SLEEP-WAKE RHYTHM. WE PURSUE AN ADDITIONAL EXPLORATORY GOAL WITH ADDING ACTIGRAPHY: SUPPLEMENTAL DATA IN ADDITION TO THE ALREADY APPROVED EEG WITH REGARDS TO THE NEUROPHYSIOLOGY OF MEMORY CONSOLIDATION SLEEP AFTER 40 Hz STIMULATION (COMPARED TO 21Hz AND COMPARED TO NIGHTS WITHOUT STIMULATION IN BETWEEN): THE DEVICE IS WORN ON THE WRIST (LIKE A WATCH), IT IS LIGHTWEIGHT, AND IT DOES NOT NEED TO BE RECHARGED DURING THE SCHEDULED WEARING PERIOD.
 
7. MOTOR THRESHOLDING (TEXT FROM MODIFICATION): SINCE THE ORIGINAL DESIGN OF THE STUDY, NEW EVIDENCE SUGGESTS AN INTERESTING RELATIONSHIP BETWEEN THE EFFECT OF tACS AND BRAIN EXCITABILITY MEASURED WITH SINGLE PULSE TMS. WE WILL THEREFORE MEASURE CORTICAL EXCITABILITY BY PERFORMING MOTOR THRESHOLDING USING SINGLE PULSE TMS (TRANSCRANIAL MAGNETIC STIMULATION) DURING VISIT 2. THE PROCEDURE TAKES ONLY A FEW MINUTES, AND ONLY SINGLE PULSES WILL BE APPLIED UNTIL A MOTOR RESPONSE RESULTS AT THE HAND (=5 OUT OF 10 EVOKED POTENTIALS OF FIRST DORSAL INTEROSSEUS MUSCLE =50mV PEAK-TO-PEAK).
 
8. (PLANNING) PREGNANCY IS REASON FOR EXCLUSION
 | |
|--|--|--|

| | | | |
|------------|--|--|--|
| 1.3 | | ADAPTED OUTCOMES TO THE VERSION SUBMITTED TO THE IRB (=ADDING AIM 8). CHANGING TYPOS IN THE SCHEDULE. | |
| 1.4 | | - EXCLUSION CRITERIA: PSQI > 5 (INSTEAD OF >6) - SESSIONS: 8AM-12PM, 12PM-6PM | |

Table of Contents

| | |
|---|----|
| Table of Version Changes | 2 |
| Statement of Compliance | 7 |
| Table of Abbreviations | 8 |
| 1. Protocol Synopsis | 9 |
| 2. Introduction | 12 |
| 2.1. Background Information | 12 |

This study will be conducted as specified in the protocol and in accordance with the *International Conference on Harmonisation Guidelines for Good Clinical Practice* (ICH E6) and the *Code of Federal Regulations on the Protection of Human Subjects* (45 CFR Part 46).

The protocol, informed consent form(s), recruitment materials, and all participant materials will be submitted to the *Institutional Review Board* (IRB) for review and approval. Approval of both the protocol and the consent form must be obtained before any participant is enrolled. Any amendment to the protocol will require review and approval by the IRB before the changes are implemented to the study. In addition, all changes to the consent form will be IRB-approved; a determination will be made regarding whether a new consent needs to be obtained from participants who provided consent, using a previously approved consent form.

If required by the IRB, the master protocol document, informed consent form(s), recruitment materials, and all participant materials will be submitted to the *Scientific Review Committee* (SRC) prior to IRB review (research.unc.edu/clinical-trials/src).

The statistical analysis plans will be consistent with guidance in CONSORT Statement [1] or STROBE Statement [2], ICMJE recommendations [3], the 2016 and 2019 statements of the American Statistical Association [4,5], and recommendations in *Nature* [6,7].*

All personnel involved in the conduct of this study have completed human participants protection training.

* [1] www.consort-statement.org

[2] www.strobe-statement.org

[3] www.icmje.org

[4] Wasserstein RL, et al. (2016), The ASA's Statement on p-Values, *The American Statistician*, 70:2, 129-133

[5] Wasserstein RL, et al. (2019), Moving to a World Beyond $p < 0.05$, *The American Statistician*, 73:sup1, 1-19

[6] Amrhein, et al. (2019) Scientists rise up against statistical significance, *Nature* 567, 305-307

[7] Editorial (2019) It's time to talk about ditching statistical significance: Looking beyond a much used and abused measure would make science harder, but better. *Nature* 567, 283-283.

Table of Abbreviations

| | |
|----------|---|
| AE / SAE | adverse event / serious adverse event |
| CFR | U.S. Code of Federal Regulations (www.eCFR.gov) |
| CI | confidence interval |
| CIOMS | Council for International Organizations of Medical Sciences (cioms.ch) |
| CoC | certificate of confidentiality |
| CONSORT | Consolidated Standards of Reporting Trials (www.consort-statement.org) |
| CRF | case report form |
| CRO | contract research organization |
| CSCC | UNC Collaborative Studies Coordinating Center (sites.cscc.unc.edu/cscc) |
| CT.gov | ClinicalTrials.gov website |
| DCC | data coordinating center |
| DSMB | data and safety monitoring board |
| eCRF | electronic case report form |
| eCTD | electronic common technical document |
| EEG | Electroencephalography/electroencephalogram |
| DOH! | I need to delete this example term (and others not used in this protocol) from this table |
| FDA | U.S. Food and Drug Administration (www.fda.gov) |
| GCP | good clinical practice |
| HIPAA | U.S. Health Insurance Portability and Accountability Act (www.hhs.gov/hipaa) |
| ICF | informed consent form |
| ICH | International Council for Harmonization (www.ich.org) |
| ICMJE | International Committee of Medical Journal Editors (www.icmje.org) |
| IDE | investigational device exemption |
| IDS | UNC Investigational Drug Services (uncids.web.unc.edu) |
| IND | investigational new drug application |
| IRB | institutional review board |
| MAR | missing at random criterion |
| MCAR | missing completely at random criterion |
| MNAR | missing not at random criterion |
| MICE | multiple imputation by chained equations |
| MOP | manual of procedures |
| MPD | master protocol document |
| N | number of enrolled participants |
| NDA | new drug application |
| OCT | UNC Office of Clinical Trials (research.unc.edu/clinical-trials) |
| OHRP | Office for Human Research Protections |
| PHI | protected health information |
| PI | principal investigator |
| PRC | UNC Oncology Protocol Review Committee (UNCLineberger.org/protocolreview) |
| QA | quality assurance |
| RCT | randomized controlled trial |
| REDCap | Research Electronic Data Capture system |
| SD | standard deviation |
| SE | standard error |
| SOP | standard operating procedures |
| SRC | UNC Scientific Review Committee (research.unc.edu/clinical-trials/src) |
| STROBE | Strengthening Reporting of Observational Studies in Epidemiology (www.strobe-statement.org) |
| tACS | Transcranial Alternating Current Stimulation |
| TraCS | N.C. Translational and Clinical Sciences Institute (tracs.unc.edu) |
| UNC | The University of North Carolina |
| UNCH | UNC Hospitals |

1. Protocol Synopsis

| | |
|-----------------------------------|---|
| Title | Effects of Transcranial Alternating Current Stimulation (tACS) on Memory Recall and Sleep-EEG in Healthy Elderly Participants (SUPERCHARGE) |
| Study Description | 
The purpose of this clinical trial is to investigate the feasibility and efficacy of non-invasive transcranial alternating current stimulation (tACS) at gamma frequency in enhancing memory recall and modulating sleep network dynamics measured by at-home electroencephalography (EEG) in healthy elderly people. Eligible participants will first collect sleep EEG at home for one night to acclimate to the data collection during sleep. Participants are then randomized into first undergoing either gamma-tACS or control tACS. Stimulation is administered in the lab during a cognitive testing battery that includes memorizing items. After a night of sleep with EEG at home, participants return to the lab the following day to measure memory recall. Memory recall is tested again by telephone five days later. This sequence of encoding during stimulation in the lab, sleep EEG at home for one night, and memory recall is then repeated for the other stimulation condition about a week later. An actigraphy watch (accelerometer) is worn during the whole study period.
 |
| Specific Aims (objectives) | 
Aim 1: To establish acceptability of cognitive testing during tACS in healthy elderly participants.
 
Aim 2: To investigate the effect of a single session of gamma-tACS (compared to control tACS) on verbal memory (a) and associative memory (b) performance during stimulation, on the day after stimulation and after five days.
 
Aim 3: To establish feasibility of at-home use of a single-channel EEG device during one night (a) and acceptability during three nights (b).
 
Aim 4: To investigate the effect of a single session of gamma-tACS (compared to control tACS) on the amount of sleep spindles (a) and slow wave sleep (b) occurring during the night after the intervention.
 
Aim 5: To see if there is a correlation between memory recall performance and sleep EEG features (especially spindles, slow waves).
 
Aim 6: To investigate the effect of a single session of gamma-tACS (compared to control tACS) on a letter fluency task (a), executive functioning (Stroop Test (b), Trail Making Test (c)) and attention (Attentional Performance, TAP (d)).
 
Aim 7: To see if the motor activity pattern (measured by actigraphy) changes after stimulation/type of stimulation.
 
Aim 8: To investigate if there is a relationship between the brain excitability derived from the subjective effect of tACS and the motor threshold measured by TMS.
 |
| Target Population | 
Inclusion Criteria
 
 • >50 years old 
Exclusion Criteria
 
 • Implanted device or metal in head (including cochlear implant or other hearing aid), cardiac pacemaker or any other powered medical device • Known neurological disease from history (epilepsy, sleep disorder (insomnia, sleep apnea, restless legs syndrome, |

| | |
|----------------------|--|
| | 
parasomnia), stroke or transitory ischemic attack, cognitive impairment, neurodegenerative disease (for example Alzheimer's disease, Parkinson's disease or amyotrophic lateral sclerosis), immune-mediated disease of the central nervous system, chronic infectious brain disease, brain tumor, traumatic brain injury with loss of consciousness and/or intracranial bleeding, chronic pain with the need for daily analgesic use)
 
 • Positive screening for epilepsy (questionnaire) • Pathological Montreal Cognitive Assessment (MoCA <26/30 points) • Brain surgery in the past (lifetime) • Known psychiatric disorder from history (schizophrenia (lifetime), obsessive compulsive disorder (OCD; lifetime), borderline personality disorder (lifetime), anxiety disorder (lifetime), bipolar disorder (lifetime), psychosis (lifetime), eating disorder (lifetime), depression (within the last three months) • Positive screening for anxiety disorder (GAD-7 \geq10/21 points) or positive screening for depression (PHQ-9 \geq5/27 points) • Known other relevant medical condition from history (moderate to severe chronic obstructive pulmonary disease (COPD), abnormal kidney function (defined as estimated Glomerular Filtration Rate <60ml/min), current liver disease (defined as hepatitis and/or liver cirrhosis), cancer, diabetes mellitus, cardiac disease (heart failure, myocardial infarct, atrial fibrillation and revascularization – all within the last three months) • Working in night shifts or going to bed after midnight on 3 or more nights per week • Positive screening for sleep disorder (PSQI $>$5/21 points) • Psychotropic treatment or illegal drugs (including cannabis) within the last three months • Indication for alcohol use disorder: AUDIT score (Alcohol Use Disorders Identification Test; screening for unhealthy alcohol use) \geq7 for females and for males \geq 65 years or \geq8 for males <65 years • Not willing to abstain alcohol at least 24 hours before each study visit • Women who want to become pregnant, are pregnant, plan to seek or are seeking fertility treatment 
Reason for immediate early termination of participation
 
 • Epileptiform activity in 128-channel EEG on the first day |
| Numbers of Enrollees | This pilot study requires n = 28 participants who complete all aspects of the protocol. Participants are recruited and enrolled until this target is reached. We anticipate screening up to 100 participants and enrolling up to 50 participants. |

| | |
|--|---|
| Intervention | 
This is a single-center prospective interventional control controlled cross-over pilot study.
 
The intervention consists of the application of tACS stimulation in the gamma-frequency range during approximately one hour of cognitive testing.
 |
| Outcome Measures | 
Aim 1: Cognitive testing during tACS completed in >80% of participants.
 
Aim 2: Participants will memorize 15 words ("Rey Verbal Learning Test", (a)) and 8 word-pairs (associative verbal memory, (b)) during gamma-tACS and control tACS. They will be required to recall the words after a short delay on the same day, on the day after and after 5 days ("ultra-delayed recall"). The number of correctly remembered words (a) and word-pairs (b) will be recorded.
 
Aim 3: Feasibility (a) will be considered feasible if the device has been worn for at least 4 hours during the first night for >/= 80% of participants. Acceptability (b) will be considered as given if the device has been worn for at least 4 hours during each of the three nights in >/=80% of participants.
 
Aim 4: Amount of sleep spindles (a) and slow wave sleep (b) during sleep recording.
 
Aim 5: Exploration of correlation between memory recall performance and sleep EEG features (especially spindles, slow waves). Difference in recall scores (verum versus sham tACS) will be correlated with differences in sleep EEG features (verum versus sham tACS).
 
Aim 6: For (a) the number of correct words, of perseverations and of rule breaks will be calculated. For (b) and (c) time for test completion and errors will be calculated. For (d) percentile ranks for the following subtests will be calculated: Alertness, Go/NoGo, Divided Attention, Visual Scanning.
 
Aim 7: Exploration of correlation between amount of motor activity/inactivity phases (measured by actigraphy watch) and stimulation versus no stimulation as well as gamma- versus control stimulation.
 
Aim 8: Exploration of correlation between the TMS motor threshold and the maximal tolerated amplitude (according to the subjective symptoms) for tACS.
 |
| Statistical Analysis Plans for Each Aim | 
Aim 1: Proportion (percentage and 95% confidence interval) of participants with completed cognitive testing during stimulation study session.
 
Aim 2: Comparison of memory and associative testing after stimulation and sham on individual and group level using ANCOVA.
 
Aim 3: Proportion (percentage, 95% confidence interval) of participants with at least four hours of EEG-data in the first night (a).Proportion (percentage,
 |

| | |
|-------------------------------|--|
| | 95% confidence interval) of participants who successfully collected at least four hours of EEG for all three study nights (b). Aim 4: Comparison of sleep spindles (a) and slow wave sleep (b) derived from sleep EEG for verum versus control tACS using ANCOVA. Aim 5: Exploratory investigation of correlations (Pearson's) between stimulation induced changes in memory recall performance and sleep EEG features. Aim 6: Comparison of test results after stimulation and sham on individual and group level using ANCOVA. Aim 7: Exploratory investigation of correlations (Pearson's) between changes in motor activity pattern before and after stimulation. Aim 8: Exploratory investigation of a correlation (Pearson's) between the level of the TMS motor threshold and the tolerated tACS level (lower level from 21 Hz and 40 Hz, based on subjective symptoms). |
| Study Duration | 1 year |
| Participation Duration | 2 weeks |
| Enrollment Duration | 6 months |

2. Introduction

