2.1. Background Information

The decline of cognitive functions, especially memory, is a common complaint, both during the normal ageing process and in dementia (1): More than half of the population will probably face such symptoms in their second half of life.

Parallel to cognition, sleep architecture changes in older age, including a reduction of slow wave sleep (for a review see (2)). Given the importance of sleep for the consolidation of memory (for a review see (3) and (4)) and its role in reducing cellular waste (including amyloid, the pathological hallmark of Alzheimer's disease) via the glymphatic system (5), it seems plausible that a deterioration of sleep in older individuals partly explains a worsening of memory functions.

Despite the importance of the problem, there is still a lack of effective measures against cognitive decline in ageing individuals.

However, advances in neuroscience within the last few years have given us an increasingly detailed understanding of the oscillations of brain activity in neural circuitries associated with cognitive processes, offering possibilities of influencing them.

Transcranial alternating current stimulation (tACS) is an established, safe way to non-invasively modulate oscillations in neuronal networks and thus potentially restore and improve the associated cognitive functions (for a

recent review of applying tACS to improve cognition in various contexts see (6), for tACS to improve memory in healthy adults see (7)).

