| Montreal Cognitive Assessment (20) | Ordinal 0-30 | 0 | All | Screening |
| Epilepsy Screening (21) | Binary | 0 | All | Screening |
| Handedness Questionnaire (22) | Laterality Index | 0 | All | Covariate uses |
| Behavioral Inhibition and Behavioral Activation Self Report Scales (BIS/BAS) (23) | Ordinal, 4 subscales: BIS (7 to 28) BAS drive (4-16) BAS fun-seeking (4-16) BAS reward (7-20) | 0 | All | Covariate uses |
| Basic Sleep Habits | hh:mm; hours/min | 0 | All | Covariate uses |
| Stimulation conditions | | | | |
| Epileptiform activity in EEG | Binary | 0 | All | Early termination of study participation |
| Karolinska Sleepiness Scale (24) | Ordinal 1-10 | D1A, D2A, D1B, D2B | Aim 2 | Covariate use |
| PANAS (Positive and Negative Affect Schedule) (25) | Ordinal 20-100 | D1A, D2A, D1B, D2B | Aim 2 | Covariate use |
| Sleep quality night before | Categorical (nominal) | D1A, D2A, D1B, D2B | Aim 2 | Covariate use |
| Cognitive testing | | | | |
| Completed | Binary | D1A, D2A, D1B, D2B | Aim 1 | Primary outcome |
| Delayed and ultra-delayed recall from Rey Auditory Verbal Learning Test (RAVLT) (26) and from word | Ratio (number of correct words); number of correct words for trials 1-5 (=learning), for trial 6 ("interference") and for trial 7 ("recall"); | D1A, D2A, PA, D1B, D2B, PB | Aim 2, Aim 5 | Primary outcome |

| | | | | |
|---|---|----------------------------|-------|---|
| association test; RAVLT encoding | number of confabulations and perseverations in total) | | | |
| Time from encoding of RAVLT and word association test to delayed and ultra-delayed recall | Interval (hh:mm) | D1A, D2A, PA, D1B, D2B, BP | Aim 2 | Covariate use |
| Time from encoding of word association test to delayed and ultra-delayed recall | Interval (hh:mm) | D1A, D2A, PA, D1B, D2B, BP | Aim 2 | Covariate use |
| RAVLT | Ratio (number of correct words for trials 1-5 (=learning), for trial 6 ("interference") and for trial 7 ("recall"); number of confabulations and perseverations in total) | D1A, D1B | Aim 2 | Covariate use |
| Word association test | Ratio (number of correct words for trials 1-4) | D1A, D1B | Aim 2 | Covariate use |
| Letter Fluency (28) | Ratio (number of correct words, number of perseverations and number of rule breaks) | D1A, D2A, D1B, D2B | Aim 6 | Secondary outcome |
| Stroop Color and Word Test (29) | Interval (sec), ratio (errors) | D1A, D2A, D1B, D2B | Aim 6 | Secondary outcome |

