| Trail Making Test A and B (30) | Interval (sec), ratio (errors) | D1A, D2A, D1B, D2B | Aim 6 | Secondary outcome |
| Test of Attentional Performance (TAP) (31) | Interval, ratio (Alertness: Percentile rank of median reaction time for correct responses, percentile rank of standard deviation; Go/NoGo: Percentile rank of median reaction time for correct responses, percentile rank of standard deviation, percentile rank of errors; Divided Attention: Percentile rank of median reaction time for correct responses, percentile rank of standard deviation, percentile rank of errors, percentile rank of omissions; Visual Scanning: Percentile rank of median of critical and non-critical, respective standard deviation, omissions) | D1A, D2A, D1B, D2B | Aim 6 | Secondary outcome |
| Sleep EEG | | | | |
| First night with ≥4 hours of recording | Binary (hh:mm) | N1 | Aim 3 | Primary outcome; early termination of study participation if <4 hours |
| EEG worn for ≥4h hours in 3/3 nights | Binary (nights) | N1, N2A, N2B | Aim 3 | Primary outcome |

| | | | | |
|---|-------------------------------------|--------------------|--------------|---------------------|
| Sleep latency | Minutes | N1, N2A, N2B | Aim 4, Aim 5 | Covariate use |
| Sleep efficiency | % | N1, N2A, N2B | Aim 4, Aim 5 | Covariate use |
| Sleep spindles, slow wave sleep | Amount/hour | N1, N2A, N2B | Aim 4, Aim 5 | Primary outcome |
| Subjective tolerability of headband | Binary, nominal | N1, N2A, N2B | Aim 3 | Exploratory use |
| Actigraphy | | | | |
| Motor activity/24 hours, resting time for sleep | %, hours | N2A, D2A, N2B, D2B | Aim 7 | Exploratory outcome |
| Thresholding | | | | |
| TMS motor threshold | % MSO (maximal stimulator output) | D2A | Aim 8 | Exploratory outcome |
| tACS thresholding | mA (lower value of 21 Hz and 40 Hz) | D2A | Aim 8 | Exploratory outcome |
| Safety Monitoring | | | | |
| AEs and SAEs documentation | Events | All | All | Safety monitoring |

¹ Units of measurement or the scale.

² Occasions of evaluation or retrieval:

S = Screening

0 = Enrollment and Baseline

N1 = Night 1

D1A = Day 1 in Intervention A

N2A = Night 2 in Intervention A

D2A = Day 2 in Intervention A

PA = Phonecall in Intervention A

D1B = Day 1 in Intervention B

N2B = Night 2 in Intervention B

D2B = Day 2 in Intervention B

PB = Phonecall in Intervention B

³ The specific aims in which the variable will play a role in data analyses.

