7.4. Study Visits

Visit 2 (day after Visit 1; afternoon/early evening, i.e. start between 12pm and 6pm)

1. Questioning whether there has been any use of alcohol, psychotropic substances or illicit drugs during the past 24 hours. If yes, study participation is terminated.
2. Questions to assess current sleepiness and mood, as this may affect the results of further testing:
 - 2.1 Questions for sleep quality the night before
 - 2.2 Karolinska Sleepiness Scale (24)
 - 2.3 Positive And Negative Affect Schedule (PANAS) (25)
3. Motor thresholding by TMS.
4. Thresholding individual tACS amplitude.
5. Gamma-tACS or control stimulation (according to randomization) during the following cognitive tests, presented on a computer screen (2 minutes of resting EEG without stimulation after each test; total duration approximately 40 minutes):
 - 5.1 Rey Auditory Verbal Learning Test (RAVLT, version 1) (26)
 - 5.2 Letter Fluency; letters F, A, S (28)
 - 5.3 Stroop Color and Word Test (29)
 - 5.4 Trail Making Test A and B (30)

- 5.5 Word association test; version 1
- 5.6 Four subtests of the Test of Attentional Performance (TAP) (31): Alertness, Go/Nogo, Divided Attention, Visual Scanning
- 5.7 RAVLT delayed recall
6. Evaluation of side effects with open question (“Did you feel anything particular or note anything special during this session?”)
7. The participant will be given the sleep diary for the second night with the EEG headband.

Visit 3 (day after Visit 2; morning, i.e. start between 8am and 12pm)

1. Questioning whether there has been any use of alcohol, psychotropic substances or illicit drugs during the past 24 hours. If yes, the participant is excluded.
2. Questions to assess current sleepiness and mood, as this may affect the results of further testing:
 - 3.1 Questions for sleep quality the night before
 - 3.2 Karolinska Sleepiness Scale
 - 3.3 Positive And Negative Affect Schedule (PANAS)
3. Cognitive follow-up testing
 - 4.1 RAVLT “ultra-delayed” recall; version 1
 - 4.2 Letter fluency; letters B, H, R
 - 4.3 Stroop Color and Word Test (SCWT)
 - 4.4 Trail Making Test Part A and B
 - 4.5 Word association recall; version 1
 - 4.6 Four subtests of the Test of Attentional Performance (TAP): Alertness, Go/NoGo, Divided Attention, Visual Scanning

Visit 4 (telephone; 5 days after Visit 2)

Performed by telephone.

1. Assessment of adverse events.
2. RAVLT “ultra-delayed” recall; version 1.
3. Word association recall; version 1.

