To evaluate the effect of gamma-tACS compared to control stimulation on sleep EEG. Differences (individual level and group level, statistical tests as mentioned above) of sleep latency (minutes from lights out to sleep onset), sleep efficiency (sleep duration in relation to time spent in bed), sleep spindle frequency (maximum number per hour) and slow wave activity (maximum minutes of slow wave sleep per hour).

The statistical method will be the same as for Aim 2.

Null hypothesis: Sleep EEG does not change after gamma-tACS compared to the night after control stimulation.

Alternative hypothesis: There is a higher amount of sleep spindles and/or slow wave sleep after gamma-tACS (compared to the control).

Plans for Aim 5.

To investigate whether there is a correlation (Pearson's) between the stimulation-induced changes in cognitive testing scores and sleep EEG features after gamma-tACS versus after control stimulation (on individual and group level). This is an exploratory analysis.

Plans for Aim 6.

Comparison of cognitive test results after stimulation and sham on individual and group level using ANCOVA (see CT.gov). This is an exploratory analysis.

Plans for Aim 7. To investigate whether there is a correlation (Pearson's) between the stimulation-induced changes in motor activity features (according to the wristband accelerometer results) after stimulation in general and after gamma-tACS versus after control stimulation (on individual and group level). This is an exploratory analysis.

Plans for Aim 8.

To investigate whether there is a correlation (Pearson's) between the motor threshold (TMS) and the subjective symptoms during tACS. This is an exploratory analysis.

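### Aim 5 correlates sleep EEG with recall differences that are not adjusted for recall before the night, so encoding and overnight change are mixed and the result cannot be read as a sleep-consolidation link

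*Combined protocol and SAP*

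**What the plan says.** The synopsis (Outcome Measures, Aim 5) states: "Difference in recall scores (verum versus sham tACS) will be correlated with differences in sleep EEG features (verum versus sham tACS". The scores are plain counts, from Aim 2 of the same table: "The number of correctly remembered words (a) and word-pairs (b) will be recorded". On timing, it adds: "They will be required to recall the words after a short delay on the same day, on the day after and after 5 days".

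In section 4.3, Table 1, the row for delayed and ultra-delayed recall reads: "D1A, D2A, PA, D1B, D2B, PB | Aim 2, Aim 5 | Primary outcome". The footnote gives "D1A = Day 1 in Intervention A". That is the stimulation and encoding day, before the night coded N2A. D1B is the same for the other condition. Separate Table 1 rows list the day-1 RAVLT and word association learning scores as covariates for Aim 2 only.

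Section 8.3 plans a Pearson correlation between "the stimulation-induced changes in cognitive testing scores and sleep EEG features after gamma-tACS versus after control stimulation". It names no recall occasion and no adjustment.

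The pre-sleep RAVLT measure exists: section 7.4 lists "5.7 RAVLT delayed recall" at Visit 2 and the version 2 counterpart at Visit 5. For word-pairs, section 7.4 schedules no separate same-day delayed recall, but Table 1 records learning trials 1 to 4.

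**The concern.** The protocol's interest in sleep comes from memory consolidation. Section 2.1 begins that argument with "Given the importance of sleep for the consolidation of memory", and section 4.1 refers to consolidation during slow wave sleep. A reader of Aim 5 will therefore tend to take a correlation with spindles or slow wave sleep as evidence about consolidation.

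The planned variables cannot carry that reading. Recall on the stimulation day precedes the recorded night and cannot be a result of it. Next-day and 5-day recall still contain everything that made one list better learned than the other. Some of this is built into the design: RAVLT and word-pair version 1 are used at Visit 2 and version 2 at Visit 5, so any difference in list difficulty or practice enters the gamma-minus-control difference with opposite sign in the two sequences. Section 8.3 gives Aim 2 a covariate for order and gives Aim 5 none.

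At stake is the interpretation of one exploratory analysis in a pilot that section 2.2 describes as preparation for a full-scale RCT. A true overnight association could be missed, or an encoding effect could pass for a sleep effect.

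**Working it through.** **Inputs from the documents.** n = 28 completers (section 5.1) and a threshold of 0.05 (section 8.1). No SD, detectable correlation or power is given for Aim 5.

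**The plan's own figure.** Section 5.1 derives 28 from dz = 0.5, power 0.80 and alpha 0.05. A paired t-test with the noncentral t distribution needs 27 one-sided (power 0.825 at 28) and 34 two-sided (power 0.723 at 28). So 28 is reproduced approximately as a one-sided paired comparison. It was not set for Aim 5.

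**Assumptions.** Two-sided 0.05. Let P be the gamma-minus-control difference in pre-sleep recall, C the same difference in overnight change, and S the sleep-EEG difference. The next-day recall difference is P + C. P and C are independent, S correlates with C at r = 0.5, and k = SD(P)/SD(C).

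**Benchmarks at n = 28.** With Fisher's z, power = Φ(5·atanh(r) − 1.96) plus a negligible lower tail, since √(28 − 3) = 5. For r = 0.5 this gives 0.78. The critical |r| is 0.374, and 80% power needs r = tanh((1.96 + 0.842)/5) = 0.51.

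**Attenuation, if S is unrelated to P.** The correlation of S with unadjusted next-day recall is 0.5/√(1 + k²):

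| k | r, next-day recall unadjusted | power |
|---|---|---|
| 0.5 | 0.5/√1.25 = 0.45 | 0.67 |
| 1 | 0.5/√2 = 0.35 | 0.46 |
| 2 | 0.5/√5 = 0.22 | 0.21 |

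Under the same assumptions, the correlation of S with recall before the night is 0.

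**Inflation, if stimulation shifts both encoding and sleep.** Suppose S correlates with P at 0.3 and not at all with C. Unadjusted next-day recall then shows r = 0.3k/√(1 + k²): 0.13 at k = 0.5, 0.21 at k = 1 and 0.27 at k = 2. None of this is overnight change.

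**Effect of recall error.** Take k = 1, r = 0.5, and error variance v (relative to the variance of P) in each recall difference.
- Unadjusted: r = 0.5/√(2 + v).
- Simple change score: r = 0.5/√(1 + 2v).
- Next-day recall adjusted for pre-sleep recall: r = 0.5/√(2 + v − 1/(1 + v)), with √(28 − 4) in place of √(28 − 3) for the power.

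| v | unadjusted r (power) | simple change r (power) | adjusted r (power) |
|---|---|---|---|
| 0.25 | 0.33 (0.41) | 0.41 (0.58) | 0.42 (0.58) |
| 0.5 | 0.32 (0.37) | 0.35 (0.46) | 0.37 (0.48) |
| 1 | 0.29 (0.32) | 0.29 (0.32) | 0.32 (0.36) |

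Adjustment is at least as good as the other two throughout, but its gain over unadjusted recall falls from 0.17 to 0.04 in power. With no recall error, the lost degree of freedom lowers power from 0.78 to 0.77.

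**The case against.** The best defence is that Aim 5 never claims to measure consolidation. Section 3.5 asks whether the effects of tACS on recall go with its effects on sleep features. Because stimulation is given at encoding, that is a coherent total-effect question, and adjusting for same-day recall removes the encoding path from it. This stands. It is a reason to keep the unadjusted correlation, but not a reason to leave it as the only one, since it cannot separate the two paths.

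Second, the Table 1 row is composite: it pools tests, occasions and two aims, and need not mean that day-1 recall will itself be correlated with sleep EEG. That is fair as far as it goes. Still, the row labels the variable a primary outcome for Aim 5, and no section restricts the occasions.

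Third, section 8.1 allows additional covariates, and section 8.3 plans between-visit differences for the Aim 2 secondary outcomes. The first names no covariate. The second uses visit numbers that do not fit the schedule and is not carried over to Aim 5, where the synopsis defines the change as between stimulation conditions.

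A reader might infer that the planned correlation is necessarily diluted. The documents do not support that: they give no SDs, and inflation is equally possible. Nor do they say that a pre-sleep correlation would be reported as consolidation.

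**Conclusion.** The point holds as one of interpretation and efficiency in an exploratory aim. As written, the Aim 5 correlation mixes encoding differences with overnight change, and it should not be read as a sleep-consolidation link.

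The direction of the distortion is unknown. Its size is conditional on the assumed correlation of 0.5 and the assumed SD ratios: the loss of power runs from modest (0.78 to 0.67) to severe (0.78 to 0.21) over that range, and recall error reduces what adjustment can recover.

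It would be wrong to infer a threat to the trial's main conclusions. Aim 5 is labelled exploratory and does not set the sample size, and section 2.2 says that effects on memory and sleep are not required for the RCT to go ahead.

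**What to change.** In section 8.3, Plans for Aim 5, and to match in the synopsis and Table 1:

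- Make the main analysis the partial correlation between the gamma-minus-control difference in next-day recall and the corresponding sleep-EEG difference, adjusted for the gamma-minus-control difference in same-day RAVLT delayed recall. For word-pairs, adjust for the last learning trial. Treat 5-day recall the same way, as secondary.
- Report the unadjusted correlation alongside, labelled as the total-effect companion.
- Give D1A and D1B recall the role of covariate and negative control in Aim 5. A correlation between pre-sleep recall and the later night is not evidence of a sleep effect.
- Prefer the partial correlation to a simple change score, which loses its advantage when recall error is large.

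The cost is a few lines of text, one degree of freedom, and one more exploratory correlation per sleep feature. No new data, visits or participants are needed. Aim 2 is unchanged, because it asks for the total effect of stimulation on recall.
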